11.2 Reporting

11.2.1 Adverse Events

- AEs will be recorded from time of signed informed consent until 30 days after discontinuation of study drug(s) or until a new anti-cancer treatment starts, whichever occurs first.
- AEs will be recorded regardless of whether or not they are considered related to the study drug(s).
- All AEs will be recorded in the subject's medical record and on the appropriate study specific eCRF form within the EDC system.
- All AEs considered related to study drug(s) will be followed until resolution to \leq Grade 1 or baseline, deemed clinically insignificant, and/or until a new anti-cancer treatment starts, whichever occurs first.

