2.1.2 Secondary Objectives

- To assess the toxicity profile of androgen deprivation, darolutamide, and ipatasertib in men with high risk, localized, hormone sensitive prostate cancer that is lacking PTEN
- To measure 2 year biochemical recurrence-free survival (PSA ≤ 0.2 ng/mL) in men with high risk, localized, prostate cancer that is lacking PTEN
- To estimate rate of PSA₀ (undetectable PSA with testosterone recovery and no additional therapy) in men with high risk, localized, prostate cancer that is lacking PTEN

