Testosterone; Prostate specific antigen		X	X		X	X		X	X
DISEASE ASSESSMENT									
CT or MRI of abdomen and pelvis	X								
Bone scan	X								
TREATMENT EXPOSURE									
Ipatasertib (once daily, continuous)			X	X	X				
Darolutamide (twice daily, continuous)			X	X	X				
Androgen deprivation therapy (per standard of care)			SOC	SOC	SOC				
CORRELATIVE STUDIES (SPECIMEN COLLECTION)									
Whole blood for somatic baseline			Pre-C1						
Archival biopsy slides ¹²	X								
Research blood/plasma collection ¹⁴			Pre-C1,C2			X			
Prostatectomy specimen							X		
BANKING SAMPLES (SPECIMEN COLLECTION)									
Whole Blood			Cycle 1						
Unstained Slides (if available)			Cycle 1				X		
Serum and Plasma			Cycle 1					X	
FOLLOW-UP									
Survival status, evidence of biochemical progression									X

Key to Footnotes: Phase II Neoadjuvant Cohort

¹If screening (baseline) labs were performed within 7 days of C1D1 of treatment, these do not need to be repeated.

²Visits should occur every 28 days. A window of 3 days will be applied to all treatment study visits; for safety follow-up visit a 7-day window will apply.

³Prostatectomy will occur within 28 days (± 14 days) of end of the sixth cycle.

⁴A safety follow-up visit will occur 30 days (± 7 days) after the last dose of treatment.

⁵Subjects without documented disease progression will be followed for disease progression every 6 months for 2 years.

⁶Medical history to include smoking history, trial awareness question prior IHC and genetic testing of tumor tissue.

⁷Diagnosis and staging to include pathology report and Tumor Node Metastasis (TNM) staging.

d. Staging may be captured from initial diagnosis.

e. Repeat abdominal imaging to confirm stage must be performed within 90 days of trial initiation.

f. Staging will be based on the 8th edition of the AJCC Cancer Staging Manual.

⁸Vital signs to include blood pressure, weight, and height (screening only) and ECOG performance status

⁹Laboratory assessment will be performed prior to treatment initiation as noted and every cycle thereafter at clinic visits during treatment periods. Following the conclusion of treatment, testosterone and PSA assessment will be continued with each visit during long term follow up at the interval noted above.

¹⁰CMP to include sodium, potassium, chloride, creatinine, blood urea nitrogen; liver function tests (LFTs) to include AST, ALT, total bilirubin, alkaline phosphatase

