7.1 Safety Follow-up Evaluations

A safety follow-up visit should occur when subjects permanently stop study treatment for whatever reason (toxicity, progression, or at discretion of site investigator) and should be performed 30 days (± 7 days) after the last dose of treatment. Subjects who have an ongoing \geq grade 2 or serious AE (SAE) at this visit will continue to be followed until the AE resolves to \leq Grade 1 or baseline, is deemed clinically insignificant, and/or until a new anti-cancer treatment starts, whichever is earlier.

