11.2.3 Serious Adverse Events (SAEs)

11.2.3.1 Site Requirements for Reporting SAEs to Big Ten CRC Administrative Headquarters

- SAEs will be reported from time of study drug administration until 30 days after discontinuation of study drug(s) or until a new anti-cancer treatment starts, whichever occurs first.
- SAEs will be reported on the SAE Submission Form and entered in the SAE tab in the EDC system.
- SAEs include events related and unrelated to the study drug(s).
- All SAEs will be recorded in the subject's medical record and on the appropriate study specific eCRF form within the EDC system.
- All SAEs regardless of relation to study drug will be followed until resolution to \leq Grade 1 or baseline and/or deemed clinically insignificant and/or until a new anti-cancer treatment starts, whichever occurs first.

For SAEs and AESIs assessed as at least possibly related to the study drug(s) or assessed as unknown relation, the site will submit the completed SAE Submission Form (see Documents/Info tab in the EDC) to Big Ten CRC AHQ within **1 business day** of discovery of the event. The form will be sent electronically to Big Ten CRC AHQ at [contact]. The site investigator is responsible for informing the IRB and/or other local regulatory bodies of the SAE as per local requirements.

The original copy of the SAE Submission Form and the email correspondence must be kept within the study file at the study site.

Once the SAE has resolved, sites must electronically submit a follow up SAE Submission Form within a reasonable timeframe to Big Ten CRC AHQ at [contact].

SAEs assessed as unrelated to study drug will entered in to the EDC within 30 days of awareness of the event.

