12.7.2 Phase II (Neoadjuvant Cohort)

In the Phase II neoadjuvant cohort, if after 9 evaluable patients there are no patients with exceptional response (defined as pCR or MRD), accrual will halt due to lack of efficacy. Accrual will not pause while the 9th patient is on therapy, so additional patients may accrue prior to pathologic evaluation of the 9th radical prostatectomy.

For the Phase II neoadjuvant cohort, an additional *early stopping rule for safety* will also be followed throughout the duration of the study. If, at any time, 2 or more patients experience a delay in time to prostatectomy of >28 days after the final dose of ipatasertib (i.e., a delay of > 1 week beyond the allowed timeline of 7-21 days) *due to an ipatasertib-related AE*, the study and all study treatment will be stopped. An ipatasertib-related AE is defined as an AE that is possibly, probably, or definitely related to ipatasertib. Should the study stop early, discussion of reopening the study using modified ipatasertib treatment regimens may be considered after discussion between the PI and Genentech, and after approval by the DSMC.

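### In Phase II, adverse event collection is timed from the last drug dose and not from prostatectomy, so postoperative coverage depends on scheduling and can be absent

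*Combined protocol and SAP*

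**What the plan says.** Four parts of the protocol bear on this.

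- **Collection window.** Section 11.2.1: "AEs will be recorded from time of signed informed consent until 30 days after discontinuation of study drug(s) or until a new anti-cancer treatment starts". Section 11.2.3.1: "SAEs will be reported from time of study drug administration until 30 days after discontinuation of study drug(s) or until a new anti-cancer treatment starts". In both, the earlier of the two events ends collection.
- **Safety visit.** Section 7.1: "A safety follow-up visit should occur when subjects permanently stop study treatment for whatever reason". It is set 30 days (plus or minus 7) after the last dose, as in footnote 4 of the Phase II calendar. After it, a man with an ongoing SAE or an ongoing event of grade 2 or higher "will continue to be followed until the AE resolves to" grade 1 or lower or baseline (or another listed end-point is met). This covers events already present, not new ones.
- **Surgery date.** Footnote 3 of the Phase II calendar puts prostatectomy within 28 days (plus or minus "14 days) of end of the sixth cycle". Section 12.7.2 instead speaks of a delay "beyond the allowed timeline of 7-21 days", counted from the final ipatasertib dose.
- **Use of the data.** Section 2.1.2 has a secondary objective: "To assess the toxicity profile of androgen deprivation, darolutamide, and ipatasertib in men with high risk, localized, hormone sensitive prostate cancer". Its endpoint is Grade 3 and 4 toxicity (sections 2.2.2 and 12.2.2).

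As far as the calendar table can be read from the extracted text, the AE row has no mark under surgery or long-term follow-up. The long-term column holds PSA, testosterone, survival status and biochemical progression.

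**The concern.** Every Phase II man is expected to have a radical prostatectomy shortly after study drug ends. A regimen given to prepare for surgery can do harm through the operation and recovery, so the toxicity profile should cover that period in the same way for each man. Here the clock starts at the last dose. A man operated on early has some postoperative time inside the window. A man operated on late has none, and his safety visit may come before his operation. The Grade 3 and 4 rate would then pool men with unequal postoperative observation, and the inequality would come from theatre scheduling.

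Reporting is affected too. Under sections 11.2.3.2 and 11.2.3.3, forwarding to the two companies starts from the site's SAE form. Under section 13.2, the monitoring committee sees AE and SAE summaries. A new postoperative SAE outside the window need not reach any of them.

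**Working it through.** **Inputs**

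- AE and SAE window: 30 days after last study drug (11.2.1, 11.2.3.1).
- Safety visit: 30 ± 7, so day 23 to 37 (7.1; Phase II calendar, footnote 4).
- Surgery day S, calendar: 28 − 14 = 14 to 28 + 14 = 42, from the end of cycle 6 (footnote 3).
- Surgery day S, section 12.7.2: 7 to 21, from the final ipatasertib dose.
- Assumption: ipatasertib and darolutamide both end on the last day of cycle 6 (day 0), so that the different starting points coincide.

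**Step 1. The plan's own figure.** The stopping rule in 12.7.2 is met if "2 or more patients experience a delay in time to prostatectomy of >28 days after the final dose of ipatasertib" because of an ipatasertib-related event, described as more than one week past the allowed time: 21 + 7 = 28. This reproduces.

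**Step 2. Postoperative days in the window** = max(0, 30 − S). **Safety visit in postoperative days** = 23 − S to 37 − S.

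| Surgery day S | Timeline that permits it | Postoperative days covered | Safety visit, postoperative day |
|---|---|---|---|
| 7 | 12.7.2 | 23 | 16 to 30 |
| 14 | both | 16 | 9 to 23 |
| 21 | both | 9 | 2 to 16 |
| 28 | calendar | 2 | −5 to 9 |
| 31 | calendar | 0 | −8 to 6 |
| 42 | calendar | 0 (closed 12 days earlier) | −19 to −5 |

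At S = 30 the operation day is inside the window but no later day is. From S = 31 the window has closed before surgery.

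**Step 3. Over the permitted days.**

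- Calendar, days 14 to 42: 29 days, of which 31 to 42 (12 days, 12/29 = 41%) have no coverage. Mean coverage with equal weight per day is (16 + 15 + … + 0)/29 = 136/29 = 4.7 days.
- Calendar with the 28-day wording read as a ceiling, days 0 to 42: 12/43 = 28% have none; mean 465/43 = 10.8 days.
- Section 12.7.2, days 7 to 21: none falls after day 30; mean 240/15 = 16 days.

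Equal weights describe the permitted range. They do not forecast when men will have surgery.

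**Step 4. Upper limit.** For any S of 1 or more, 30 − S is at most 29, so neither timeline gives 30 postoperative days.

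**Step 5. The two timelines side by side.** Surgery on day 35 is on schedule under footnote 3. Under 12.7.2 it is 14 days beyond the allowed time and past the 28-day threshold. The passages conflict.

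**The case against.** The strongest reply has three parts.

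**The objective concerns drug toxicity.** No perioperative morbidity endpoint is named, the analysis is descriptive (12.6.2), and about 20 men without a control arm cannot separate drug effects from surgical ones. The limit on attribution stands. It does not justify the window, because 11.2.1 records events regardless of relatedness and 11.2.3.1 includes unrelated SAEs. Section 11.1.2 excludes planned admission for resection but keeps prolonged hospitalization as serious. The protocol's own definitions thus take in postoperative events that its window can miss.

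**Section 12.7.2 puts on-time surgery inside the window and monitors delay.** This stands in part. A reader who looks only at the calendar might infer that postoperative toxicity is largely or wholly uncollected in every man. The documents do not support that: the 7 to 21 day timeline leaves 9 to 23 days, and the calendar's day 14 leaves 16. The stopping rule, however, counts only delay caused by an ipatasertib-related event and does not collect postoperative complications.

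**Other safeguards exist.** A reader might infer that postoperative deaths would be lost. Survival status is recorded in long-term follow-up, so they can be captured, though after day 30 not as reportable SAEs. A reader might also infer that prostatectomy is itself a new anti-cancer treatment, which would leave 0 days for everyone. The term is undefined, but the reading is strained: surgery is the planned end of the neoadjuvant course, and the calendar places the safety visit, with AEs marked, after it. Nor does the plan contain a test or declaration that the regimen is safe before surgery.

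Section 7.2 does not fill the gap. Its PSA and testosterone check at four weeks or more after surgery is a precondition for adjuvant or salvage therapy and not a visit for every man.

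**Conclusion.** The point holds as a gap of variable size. Collection and the safety visit are tied to the last dose, and nothing is tied to surgery. Postoperative coverage is 0 to 16 days under the calendar (2 days at its nominal day 28) and 9 to 23 days under 12.7.2. It differs between men by scheduling, stays below 30 days for surgery from day 1 onward, and is absent for surgery from day 31.

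The figures assume that both drugs end with cycle 6. If drug stops early while surgery keeps its planned date, coverage shrinks; section 6.1 does not let held or missed doses extend the preoperative course. If surgery is brought forward after early stopping, coverage need not shrink. The documents give no date for that case.

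The effect is on the secondary toxicity endpoint and on safety reporting. The primary endpoint is read at prostatectomy, so it and its power do not change. This is an inexpensive improvement that should be made. It is not a flaw that invalidates the trial.

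**What to change.** For Phase II, amend 11.2.1, 11.2.3.1, 7.1 and calendar footnote 4 as follows.

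1. Run AE and SAE collection to the later of 30 days after last study drug and 30 days after prostatectomy.
2. State that the protocol prostatectomy is not a new anti-cancer treatment for this clause. The clause can otherwise stay: 7.2 holds adjuvant or salvage therapy until results taken at least four weeks (28 days) after surgery, so such therapy should remove at most 30 − 28 = 2 days.
3. Add an AE review, by visit or phone, about 30 days after surgery.
4. Report Grade 3 or higher events separately for the preoperative and postoperative periods.
5. Reconcile footnote 3 with 12.7.2, including whether time runs from the end of cycle 6 or from the final ipatasertib dose. Which surgical timeline applies is for the investigators to settle.

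Collection would then end on day S + 30: day 44 to 72 under the calendar, or day 37 to 51 under 12.7.2, instead of day 30. The addition is S days, so 7 to 42 days (1 to 6 weeks) per man.

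The cost is that extra recording and one added AE contact in about 20 men. The reported toxicity rate may be higher, and some events will not be attributable to drug rather than surgery.

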11.2.2 Reporting of Pregnancy

- Pregnancy will be reported from time of first study drug until 30 days after discontinuation of study drug(s).
- Pregnancy will be reported to Big Ten CRC AHQ **within 1 business day** of discovery of the event.
- Pregnancy will be reported using the Big Ten CRC Pregnancy Reporting Form (see Documents/Info tab of the EDC).

The initial pregnancy notification and pregnancy follow-up will be recorded on the Big Ten CRC Pregnancy Reporting Form. The form will include an assessment of the possible relationship to the study treatment of any pregnancy outcome. Any SAE experienced during pregnancy will be reported on the SAE Submission Form.

The site will submit the completed Pregnancy Reporting Form to Big Ten CRC AHQ within **24 hours** of discovery of the event. The form will be sent electronically to [contact]. The site investigator is responsible for informing the IRB and/or other local regulatory bodies of the event as per local requirements.

11.2.3 Serious Adverse Events (SAEs)

11.2.3.1 Site Requirements for Reporting SAEs to Big Ten CRC Administrative Headquarters

- SAEs will be reported from time of study drug administration until 30 days after discontinuation of study drug(s) or until a new anti-cancer treatment starts, whichever occurs first.
- SAEs will be reported on the SAE Submission Form and entered in the SAE tab in the EDC system.
- SAEs include events related and unrelated to the study drug(s).
- All SAEs will be recorded in the subject's medical record and on the appropriate study specific eCRF form within the EDC system.
- All SAEs regardless of relation to study drug will be followed until resolution to \leq Grade 1 or baseline and/or deemed clinically insignificant and/or until a new anti-cancer treatment starts, whichever occurs first.

For SAEs and AESIs assessed as at least possibly related to the study drug(s) or assessed as unknown relation, the site will submit the completed SAE Submission Form (see Documents/Info tab in the EDC) to Big Ten CRC AHQ within **1 business day** of discovery of the event. The form will be sent electronically to Big Ten CRC AHQ at [contact]. The site investigator is responsible for informing the IRB and/or other local regulatory bodies of the SAE as per local requirements.

The original copy of the SAE Submission Form and the email correspondence must be kept within the study file at the study site.

Once the SAE has resolved, sites must electronically submit a follow up SAE Submission Form within a reasonable timeframe to Big Ten CRC AHQ at [contact].

SAEs assessed as unrelated to study drug will entered in to the EDC within 30 days of awareness of the event.

11.2.3.2 Big Ten CRC AHQ Requirements for Reporting SAEs or Pregnancies to Genentech

Upon receipt of an SAE Submission Form or Pregnancy Reporting Form from the site, Big Ten CRC AHQ will report to Genentech **within 1 calendar day**, as described in the Genentech Safety Data Exchange Agreement (SDEA). Follow-up information will be provided to Genentech as it is received from a site.

Genentech Contact:

Email: [contact].

SAEs assessed as unrelated to study drug will be reported to Genentech on a monthly basis.

11.2.3.3 Big Ten CRC AHQ Requirements for Reporting SAEs or Pregnancies to Bayer

Upon receipt of an SAE Submission Form or Pregnancy Reporting Form from the site, Big Ten CRC AHQ will report to Bayer within **24 hours** of receipt of the SAE Reporting Form/ Pregnancy Reporting Form from a site. Follow-up information will be provided to Bayer HealthCare Oncology as it is received from a site.

SAE Reports will be sent to the email address provided below. By sending to this e-mail address, the Bayer Pharmacovigilance group and the Bayer clinical operations project manager will receive copies of the reports. This process will be tested and established before the first patient is enrolled in the trial.

Bayer Safety Contacts:

[contact]

For e-mail transmission of individual SAE reports: [contact]

SAEs assessed as unrelated to study drug will be reported to Bayer on a monthly basis.

11.2.3.4 Sponsor-Investigator Responsibilities

Big Ten CRC AHQ will send a SAE summary to the sponsor-investigator **within 1 business day** of receipt of SAE Submission Form from a site. The sponsor-investigator will promptly review the SAE summary and assess for expectedness and relatedness.

11.2.3.5 Big Ten CRC AHQ Responsibilities for Reporting SAEs to FDA

Big Ten CRC AHQ has been designated to manage the Investigational New Drug Application (IND) associated with this protocol on behalf of the sponsor-investigator. Big Ten CRC AHQ will cross-reference this submission to Genentech and Bayer's parent IND at the time of submission. Additionally, Big Ten CRC AHQ will submit a copy of these documents to Genentech and Bayer at the time of submission to FDA.

Big Ten CRC AHQ will be responsible for all communication with the FDA in accordance with 21CFR312 which includes but is not limited to the 7 and 15 Day Reports, as well as an Annual Progress Report. Additionally, Big Ten CRC AHQ will submit a copy of these reports to Genentech and Bayer at the time of submission to FDA.

11.2.3.6 IND Safety Reports Unrelated to this Trial

Genentech Inc. and Bayer will provide Big Ten CRC AHQ with IND safety reports from external studies that involve the study drug(s) per their guidelines. Big Ten CRC AHQ will forward the safety reports to the sponsor-investigator who will review these reports and determine if revisions are needed to the protocol or consent. Big Ten CRC AHQ will forward these reports to participating sites **within 1 business day** of receiving the sponsor-investigator's review. Based on the sponsor-investigator's review, applicable changes will be made to the protocol and informed consent document (if required). All IND safety reports will also be made available to sites via the EDC system.

Upon receipt from Big Ten CRC AHQ, site investigators (or designees) are responsible for submitting these safety reports to their respective IRBs, as per their IRB policies.

12. STATISTICAL METHODS

12.1 Study Design

This is a phaseI/ II single armed study. Patients and caregivers will not be blinded as there is only one treatment arm.

12.2 Endpoints

12.2.1 Definition of Primary Endpoint

- Combined rate of pathologic complete response (pCR) (defined as absence of pathologic disease on hematoxylin and eosin (H&E) stain (ypT0)), or with presence of minimal residual disease (<5 mm linearly)

12.2.2 Definition of Secondary Endpoints

- Grade 3 and 4 toxicities as defined by the NCI Common Terminology Criteria for Adverse Events (NCI CTCAE) v5.
- Two year biochemical recurrence-free survival (defined as PSA \leq 0.2 ng/mL)
- Rate of PSA₀ (undetectable PSA on local institutions laboratory testing with testosterone recovery and no additional therapy)

12.3 Sample Size and Accrual

In this Simon MiniMax two-stage, single arm, phase I/II trial, we anticipate enrolling 17 evaluable PTEN-negative subjects in the primary analysis (phase II) cohort. The therapy will be considered to be of little interest in the neoadjuvant setting if the exceptional response rate is $<5\%$ (similar to AR-targeted therapy alone) and considered active if the exceptional response rate is $\geq30\%$. The study is designed with 90.5% power to detect the difference between the null hypothesis (5% or less response rate) and the alternative hypothesis (30%) with one-sided type I error of 0.05. In the first stage nine (9) patients will be recruited. If one (1) or more responses (pCR or MRD) are observed, another eight (8) evaluable patients will be recruited for a total of 17 evaluable patients. If 3 or more of 17 responses are observed, the study will be deemed a success. To account for 15% attrition, we plan to enroll 20 patients.

The Phase I de-escalation cohort will consist of patients with metastatic or nonmetastatic castrate resistant prostate cancer, with the expected sample size of 6, ***assuming no more than 1 DLT in the first 6 patients***. However, if dose reductions of ipatasertib are required, the sample size could be as large as 18.

